## STATEMENT OF COMPLIANCE

The trial will be conducted in accordance with International Council on Harmonisation Good Clinical Practice (ICH GCP), applicable United States (US) Code of Federal Regulations (CFR), and the National Institute on Drug Abuse Terms and Conditions of Award. The Principal Investigator will assure that no deviation from, or changes to the protocol will take place without prior agreement from the funding agency and documented approval from the Institutional Review Board (IRB). All personnel involved in the conduct of this study have completed Human Subjects Protection and ICH GCP Training.

The protocol, informed consent form(s), recruitment materials, and all participant materials will be submitted to the IRB for review and approval. Approval of both the protocol and the consent form(s) must be obtained before any participant is consented. Any amendment to the protocol will require review and approval by the IRB before the changes are implemented to the study. All changes to the consent form(s) will be IRB approved; a determination will be made regarding whether a new consent needs to be obtained from participants who provided consent, using a previously approved consent form.

## 1 PROTOCOL SUMMARY

[figure not shown]
### 1.1 SYNOPSIS

Title:	Following Opioid Overdose Survivors to Improve Emergency Department-Based Services: A Pilot Study
Grant Number:	R33DA045850
Study Description:	The investigators seek to conduct a pragmatic trial to assess the effectiveness of Project POINT (Planned Outreach, Intervention, Naloxone, and Treatment), an emergency department (ED)-based peer recovery coach intervention for people with opioid use disorder who present to the ED.
Objectives*:	The primary goal of this project is the establishment of POINT as an effective and scalable intervention for connecting patients to medications for opioid use disorder (MOUD). This study employs a Hybrid Type 1 effectiveness implementation design to take full advantage of current POINT expansion efforts currently happening in Indiana, with the goal of the effectiveness component described in this protocol to be testing the effectiveness of POINT under real-world conditions.
Endpoints*:	
Primary Outcome Measure:
 

1. Overdose Admissions

 
Secondary Outcomes Measures:
 

2. Medication for opioid use disorder (MOUD) engagement

3. Duration of MOUD Engagement

4. ED Admissions

5. Inpatient Hospital Admissions

6. Time to Relapse

7. Medicaid Enrollment for Participants Without Insurance

8. Child Welfare Involvement

9. Incarceration

Study Population:	Inclusion Criteria: (a) Revived from a drug overdose or admitted to the ED for an opioid-related health issue, including opioid withdrawal, abscess (from intravenous (IV) opioid use), endocarditis (from IV opioid use), or active opioid intoxication; (b) Score at least “1” on the Diagnostic and Statistical Manual of Mental Disorders (DSM)-5 for Opioid Use Disorder screening tool; (c) Eligible for discharge from a participating ED and deemed able to speak to research staff by ED staff; (d) Be 18 or older; (e) Be medically stable (i.e., cleared to leave the ED by a physician) and capable of providing consent.
Phase* or Stage:	N/A
Description of Sites/Facilities Enrolling Participants:	Indiana University (IU) Health Ball Memorial Hospital; IU Health Methodist Hospital

Description of Study Intervention/Experimental Manipulation:	POINT is a quality improvement initiative that connects trained outreach workers with ED patients who experienced a non-fatal overdose. A member of the POINT team (a peer recovery coach) meets patients after they have experienced an opioid overdose and, following a model of patient-centered care, offers them a range of evidence-based services including a brief assessment of high-risk behaviors, Hepatitis C and HIV testing, harm reduction counseling informed by motivational interviewing, and treatment referrals with follow-up to either MOUD provider, detoxification services, or an inpatient treatment setting.
Study Duration :	58 months (February 2018-December 2022)
Participant Duration:	Original data collection occurs only at enrollment and includes a single 30–60-minute structured interview. Administrative data is accessed for a 5-year period (i.e., 3 years prior to enrollment- 2 years post enrollment).

## 1.2 SCHEMA

**Figure 1: Flow Diagram including original planned enrollment\***

Note: Planned enrollment was not met after enrollment activities were temporarily stopped for several months at the busiest enrollment site due to the COVID-19 pandemic. An alternative plan using a retrospective case control design was approved by the study funder.

### 1.3 SCHEDULE OF ACTIVITIES

**Table 1: Schedule of Activities**

Procedures	Enrollment	24 months post-enrollment
Informed Consent	x	
Intake Information	x	
Patient Questionnaire	x	
Adverse Childhood Experiences (ACEs) Questionnaire	x	
Secondary Data Pull		x*

\*Secondary data are pulled at a coordinated time point at which data reflecting 24 months post-enrollment was provided for each study participant.

## 2 INTRODUCTION

### 2.1 STUDY RATIONALE

Opioid misuse and addiction are at historic heights in the United States. Despite significant need, substantial treatment and design barriers prevent many opioid users from accessing medications for opioid use disorder (MOUD), the gold standard treatment for opioid use disorder (OUD).

Planned Outreach, Intervention, Naloxone, and Treatment (POINT) is an emergency department (ED)-based intervention for engaging opioid overdose survivors into MOUD. POINT was conceptualized (and implemented at its originating site) as a critical time intervention in that it seeks to quickly mobilize support for members of a highly vulnerable population at a juncture in their lives when they are likely to be receptive to assistance (i.e., after an overdose). It accomplishes this through use of peer recovery coaches (i.e., individuals with lived experience of recovery who are trained to assist those struggling with addiction) who assist patients to navigate barriers to MOUD access after ED discharge. The use of recovery coaches in substance use disorder services is based in the premise that patients will be more receptive to sharing their personal struggles with someone who has had similar experiences. The primary goal of this project is the establishment of POINT as an effective and scalable intervention for engaging patients in MOUD through a Hybrid Type I effectiveness-implementation study. The component of this study described in this protocol is a pragmatic trial that seeks to understand the effectiveness of POINT under real-world conditions.

### 2.2 BACKGROUND

Despite its demonstrated effectiveness, the availability of providers offering MOUD is in short supply. Even where MOUD is available, a significant portion of opioid users encounter treatment and design barriers. Moreover, stigma associated with OUD and ubiquitous abstinence-only views have resulted in political roadblocks to MOUD expansion and reluctance among opioid users to seek and accept treatment. Previous studies indicate high motivation for change among opioid users, suggesting treatment avoidance is not the primary issue. As such, an increase in MOUD availability must be accompanied by innovative

approaches to help opioid users navigate obstacles blocking both access to and continued engagement in MOUD. Furthermore, people who use opioids and injection drugs inconsistently utilize health care services and are heavier users of emergency and inpatient hospital care than the general population. Therefore, the ED is in a unique position to identify, develop, and implement solutions to improve outcomes in this population. There is indeed burgeoning evidence supporting ED-based interventions for substance misuse.

At the time of this study's conceptualization, POINT was developed and operating in Indianapolis's Eskenazi Hospital. Initial results of a quality improvement study supported the intervention's potential for improving patient outcomes. The proposed project aimed to extend this work

Using settings and protocols more reflective of "real-world" conditions to study POINT will help ensure relevance of resulting findings to practice. This is particularly important considering the need for fast translation of evidence in light of the significant toll the opioid crisis is taking on the nation. The fact that POINT was already undergoing scaling activities at the time of the study's conceptualization was an important opportunity to take advantage of considering key stakeholder decisions to promote or adopt interventions are often made without regard to the scientific evidence.

## 2.3 RISK/BENEFIT ASSESSMENT

### 2.3.1 KNOWN POTENTIAL RISKS

Immediate risks to participants include: the potential that individuals may feel uncomfortable due to the sensitive nature of some of the questions that will be asked at intake or that they may become fatigued answering questions. There is also a risk of loss of confidentiality related to data collection, including the secondary data collection, should there be a breach during the collection or data transfer process (prior to the deidentification of data). In particular, individuals may be identified as a substance user. This may result in stigma for the individual. However, it is important to note that individuals will not suffer risk of criminal prosecution for drug use should their opioid overdose become known by the police, as possession, not use, is a criminally prosecutable risk in Indiana.

### 2.3.2 KNOWN POTENTIAL BENEFITS

Immediate benefits that subjects may likely gain include: the opportunity to discuss and reflect on their recent opioid use and/or overdose, a list of resources that may benefit them as someone who uses opioids (these resources will be provided even if they do not choose to participate in the study), and the opportunity to inform research that may lead to the development of stronger interventions to assist people at risk of future opioid use or overdose.

### 2.3.3 ASSESSMENT OF POTENTIAL RISKS AND BENEFITS

Sensitive data collected for this study (e.g., data pertaining to illicit drug use) are necessary to assess the proposed outcomes and examine the implementation of POINT. Study procedures aim to minimize risks associated with the collection of these data through the following ways: (a) all original data collection

will occur in a private area where others cannot overhear what is shared or see the interaction between research staff and participant; (b) all data collected during these interviews will be entered directly into Research Electronic Data Capture (REDCap to ensure secure data storage is HIPAA compliant and that only relevant research team members will have access to these data; (c) research staff will assure all participants throughout the interview that they may choose to skip any questions they do not want to answer and will also end the interview or skip the question if the participant seems distressed about sharing the information requested; (d) secondary data will be accessed through the assistance of Regenstrief Institute, an honest broker who can act as a firewall between personally identifiable health data and the researchers. Regenstrief will mask and merge the data and ensure all data are stripped of personally identifying information before delivering them to the research team. Specifically, Regenstrief will link hospital, government, substance abuse treatment, and data collected by the research staff and will keep the identification key and not share it with the research team so that information remains confidential.

### 3 OBJECTIVES AND ENDPOINTS

OBJECTIVES	ENDPOINTS	JUSTIFICATION FOR ENDPOINTS	PUTATIVE MECHANISMS OF ACTION
Primary			
Assess POINT's effectiveness at reducing overdose presentations to the emergency department.	Overdose Admissions	The primary goal of the intervention as it is designed is to reduce overdoses by linking clients to MOUD treatment.	Engagement in MOUD treatment is demonstrated to reduce overdose.
Secondary			
Assess POINT's effectiveness at improving treatment-related outcomes.	MOUD Engagement Duration of MOUD Engagement Time to Relapse ED Admissions Hospital Admissions Overdose Mortality Medicaid Enrollment	These outcomes should improve following linkage to MOUD.	MOUD treatment is associated with better treatment outcomes compared to alternative treatments for OUD.
Exploratory			
Assess POINT's effectiveness at improving recovery-related outcomes.	Child Welfare System Involvement Incarceration	These outcomes should improve as a function of treatment engagement.	MOUD treatment should result in greater abstinence from illicit opioids that will improve other areas of a patient's life.

## 4 STUDY DESIGN

### 4.1 OVERALL DESIGN

The primary objective of this pragmatic clinical trial is to replicate POINT at two new hospitals and establish POINT's effectiveness compared to standard care. In doing so, we aim to understand POINT's effect on the recovery process, including treatment and recovery outcomes and overdose. We hypothesize that POINT patients will engage in MOUD at higher rates, remain in treatment longer, and have significantly improved outcomes in comparison to the standard care group.

Hospital patients meeting the eligibility criteria at one of the two participating EDs are approached by a recovery coach or research assistant and invited to enroll in the study. Participants of the study are randomly enrolled into one of two study arms: (1) the POINT intervention arm, in which they receive ongoing recovery support services from a recovery coach or (2) the control arm, in which they receive a list of available local resources for substance use disorder from the research assistant. The study utilizes shift-level randomization, and each day of enrollment is separated into three enrollment shifts which are randomly assigned to one of the two study arms. Thus, participants' arm assignment is pre-determined by the shift in which they are discharged from the ED and enrolled into the study.

Participants are asked to complete a single structured interview at the time of their enrollment and are followed longitudinally only through administrative data, which is collected for participants from three years prior to their enrollment through two years following their enrollment.

### 4.2 SCIENTIFIC RATIONALE FOR STUDY DESIGN

The rational for a pragmatic trial is based on the fact that POINT was already demonstrating success and implemented as standard care at its originating hospital site and was under consideration to be implemented as regular care at the current study's participating hospital system at the time of study design. Given this, a standard explanatory trial was considered unfeasible. Furthermore, the funding mechanism supporting the project was designed to support research aimed at taking advantage of opioid use disorder-related initiatives that were already underway as part of Opioid State Targeted Response funding, which required researchers to design a study around already developing state plans and efforts.

### 4.3 JUSTIFICATION FOR INTERVENTION

The rational for providing recovery coach support at the patient ED bedside is because an emergency room encounter is considered a critical point in time when a person might be more motivated toward and accepting of treatment linkage. The minimal acceptable participation is engagement with the recovery coach at one time point while in the emergency department.

### 4.4 END-OF-STUDY DEFINITION

A participant is considered to have completed the study if he or she has completed the baseline assessment. The end of the study is defined as completion of this assessment.

## 5 STUDY POPULATION

### 5.1 INCLUSION CRITERIA

To be eligible for the study, a patient must:

1. Be revived from a drug overdose or admitted to the ED for an opioid-related health issue, including opioid withdrawal, abscess (from IV opioid use), endocarditis (from IV opioid use), or active opioid intoxication.
2. Score at least “1” on the opioid use disorder screening tool.
3. Be eligible for discharge from one of the two participating EDs and deemed able to speak to research staff by ED staff.
4. Be age 18 or older.
5. Be medically stable (i.e., cleared to leave the ED by a physician) and capable of providing consent.

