1. Demographics

2. Social support
3. Living arrangements
4. Drug use
5. Context of current overdose or ED admission
6. Treatment history
7. Interest in recovery services
8. Use of strategies to reduce risks related to drug use
9. HIV and Hepatitis C
10. Physical and mental health

The patient will also be asked to complete the Adverse Childhood Experiences questionnaire.

In addition to the original data collection, administrative data will be collected for each participant to assess long-term impacts regarding health, treatment, criminal justice, and child welfare involvement, as well as death records. Secondary data collection for the study will be assessed accessed from the following sources for three years prior to a participant's enrollment through two years following:

1. Indiana Network for Patient Care (*hospital and overdose admissions data*)
2. Indiana Scheduled Prescription Electronic Collection & Tracking Program (INSPECT) (*prescription information for controlled substances*)
3. Division of Mental Health and Addiction (*methadone treatment information*)
4. Indiana Office of Medicaid Planning and Policy (*Medicaid enrollment information*)
5. Indiana Department of Child Services (*child welfare involvement information*)
6. Publicly available arrest and incarceration data via (a) Indiana Department of Correction's prison incarceration search portal and (b) Marion County's inmate database search portal
7. Indiana Department of Public Health Vital Records Data (*state health/vital records*)

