#### 9.4.2 ANALYSIS OF THE PRIMARY ENDPOINT(S)

Questions	Defined/explained
Primary endpoint	
Describe how the primary endpoint is calculated, if not readily apparent	Change in Overdose Admissions: Using electronic health records, it is calculated as the total combined number of overdoses resulting in an emergency department presentation within the specified time period.
Describe the scale (nominal/binary/categorical, ordinal, interval); state if it is measured as a single endpoint/summary measure or repeated measure	binary
Describe the statistical procedure(s) that will be used to analyze the primary endpoint (e.g., multiple regression, repeated measures mixed models, logistic regression, Analysis of Covariance (ANCOVA)). Describe the covariates and factors in the model. Provide a rationale for covariates and how they will be selected to achieve a parsimonious model. If the decision to specify covariates is deferred for the SAP, indicate here.	Summarized using frequencies and percentages and then compare arms using the Fisher's exact test.
Describe how results of statistical procedure(s) will be presented (e.g., adjusted means (Least-squares means (LSMEANS)) with standard errors, odds ratios with 95% confidence intervals, prevalence rates, number-needed-to-treat)	Presented using frequencies and percentages
Describe details to check assumptions required for certain types of analyses (e.g., proportional hazards, transformations or, when appropriate, nonparametric tests)	The nonparametric Fisher's exact test is used to compare the primary endpoint.
Describe the Populations for which the analysis will be conducted, as discussed in Section 9.3, Populations for Analyses	All study participants
Describe how missing data will be handled (e.g., type of imputation technique, if any, and provide justification), and approach to handling outliers, non-adherence and lost to follow-up	We do not expect there to be a large amount of missing data due to the use of administrative datasets. However, missing values may occur when subjects die during the specified time period. Sensitivity analysis is performed by excluding subjects who die during the specified time period.

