#### 9.4.7 SUB-GROUP ANALYSES

No sub-group analyses are planned for this study.

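### The primary comparison is neither stratified nor reported by reason for the index visit, although POINT is framed around overdose survivors and entry is wider than that

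*Combined protocol and SAP*

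**What the plan says.** Three places describe POINT in terms of overdose. The title in section 1.1 is "Following Opioid Overdose Survivors to Improve Emergency Department-Based Services: A Pilot Study". The intervention description in the synopsis says that POINT "connects trained outreach workers with ED patients who experienced a non-fatal overdose". Section 2.1 calls it an "intervention for engaging opioid overdose survivors into MOUD".

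Entry is wider. Under section 5.1 a patient must "Be revived from a drug overdose or admitted to the ED for an opioid-related health issue", and the listed issues are withdrawal, abscess, endocarditis and active intoxication. The amendment history shows that this was deliberate: version 3 widened entry beyond overdose and version 4 added endocarditis.

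The broader target is also stated outright. The study description in the synopsis refers to people with opioid use disorder presenting to the ED, section 4.3 treats the ED encounter itself as the critical moment, and section 6.1.1 has the coach meeting patients after an overdose or another opioid-related problem.

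Section 9.3 analyzes everyone consented. For the primary endpoint, section 9.4.2 says "Summarized using frequencies and percentages and then compare arms using the Fisher's exact test". Section 9.4.7 says "No sub-group analyses are planned for this study", and section 9.4.9 plans no exploratory analyses. Section 9.4.1 adds a logistic model with unlisted patient characteristics and hospital as a fixed effect. Section 6.3 randomizes shifts and describes no balancing on patient factors. The enrollment interview in section 8.1 includes "Context of current overdose or ED admission".

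**The concern.** The primary endpoint is a later overdose presentation to the ED. That is the same kind of event as one entry route and not the others, so index reason is an obvious candidate prognostic factor. The plan collects it and then does not use it.

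Two things are at stake. First, if the share of index overdoses differs between arms, the difference passes straight into the unstratified comparison. Recovery coaches recruit in POINT shifts and research assistants in control shifts, and the enrollment target was missed (section 9.2). A difference in mix is therefore a practical possibility, whether by chance or through recruitment. Second, a reader drawn by the title will look for the result in overdose survivors, and as planned there will be none.

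**Working it through.** **Inputs.** From section 9.2: 356 per arm, 12% in the standard care arm, a 6-point reduction, 80% power, 5% significance. From section 9.4.2: Fisher's exact test. Assumed, because the documents do not give them: the share s of index overdoses (25%, 50%, 75%), and the rates by index reason.

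**The plan's own figure.** With the two-sided pooled-variance formula and mean rate 9%:

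n = [1.96·√(2·0.09·0.91) + 0.842·√(0.12·0.88 + 0.06·0.94)]² / 0.06² = 356 per arm.

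This reproduces the plan exactly. The planned two-sided Fisher test at 356 per arm has exact power 77.1%.

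**Imbalance in mix.** The shift in the pooled risk difference is (difference in share) × (rate after index overdose − rate in others).
- Others at 4%: 0.10 × (12 − 4) = 0.8 points.
- Others at 6%: 0.10 × (12 − 6) = 0.6 points.

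These use control rates, so they describe the shift if POINT has no effect, or if the departure in mix lies in the control arm.

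Under independent assignment the SD of the difference in share is √(2·s(1−s)/356): 3.7 points at s = 50% and 3.2 points at 25% or 75%. A 10-point difference is then 2.7 to 3.1 SD. Shift-level assignment, different recruiters and a smaller achieved sample could each make it more likely.

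**Does pooling dilute?** Index-overdose patients are set at 12% vs 6% and others at 4% in the control arm. The pooled rate in each arm is s × (rate after index overdose) + (1 − s) × (rate in others). Powers are exact two-sided Fisher, with 356 per arm pooled and 356·s per arm in the overdose stratum.

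| Share s | Overdose stratum only (n per arm) | Pooled, no effect in others (4% vs 4%) | Pooled, same risk ratio in others (4% vs 2%) |
|---|---|---|---|
| 75% | 63.7% (267) | 10.0 vs 5.5: 56.5% | 10.0 vs 5.0: 67.7% |
| 50% | 43.7% (178) | 8.0 vs 5.0: 31.3% | 8.0 vs 4.0: 55.9% |
| 25% | 21.6% (89) | 6.0 vs 4.5: 10.9% | 6.0 vs 3.0: 42.4% |

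With no effect in the others, pooling does worse than the stratum alone. With a common risk ratio the pooled ratio stays at one half and pooling does better. If 12% vs 6% holds for everyone, pooled power is 77.1%. The ordering depends wholly on an effect that the documents do not give.

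**What a split could show.** Stratum power for 12% vs 6% is the 22–64% in the second column, at the full planned sample. For an interaction of 6 points against 0, SE = √[(0.12·0.88 + 0.06·0.94)/n₁ + 2·p(1−p)/n₂], where n₁ and n₂ are the per-arm numbers of index-overdose and other patients and p is the others' rate. At s = 50% and p = 12%, SE = √(0.3732/178) = 0.0458 and power = Φ(0.06/0.0458 − 1.96) = 26%. Over the three shares the range is 19–26% with p = 12%, and 26–37% with p = 4%.

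**What stratifying does.** In the no-effect-in-others scenario, a simulated exact stratified test had power 56.6%, 31.5% and 10.9%, against 56.5%, 31.3% and 10.9% unstratified. It guards against imbalance and does not restore power.

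**The case against.** The strongest reply is that the target population really is broad. The study description, section 4.3 and section 6.1.1 say so, and the primary objective in section 3 and the hypothesis in section 9.1 are not confined to overdose survivors. On that reading the pooled comparison is the right one, and the overdose wording is a leftover from before entry was widened. This stands, and it is why the pooled test should remain primary.

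The adjusted model in section 9.4.1 could take in index reason and section 9.4.5 compares baseline characteristics. That is fair, but the covariates are not listed, so nothing commits the analysis to it.

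A 10-point imbalance would be unusual under independent assignment. That also stands. The 0.8 points is an illustration, not an expectation.

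A reader might infer that the trial cannot say whether POINT works after an overdose. The documents do not support that: the context of the visit is recorded, so a comparison in overdose survivors is possible, though unplanned and underpowered. A reader might also infer from the amendment history that most participants had no index overdose. The remark on volume there describes patients arriving at the ED, and the enrolled mix is not given.

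**Conclusion.** The point holds in a limited form. The documents name two populations. As planned, the primary comparison is not stratified by index reason and no result by index reason will be reported, although the information is collected. The size is modest: about 0.6 to 0.8 points of shift per 10-point difference in mix, under assumed control rates of 12% after an index overdose and 6% or 4% otherwise.

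It would be tempting to conclude that pooling dilutes the effect. That follows only if patients without an index overdose gain nothing, which is an assumption. With a common risk ratio the ordering reverses. Nor does any section say that the pooled result will be presented as an effect in overdose survivors; the plan simply does not guard against that reading. All power figures use 356 per arm. Section 9.2 says that this was not reached, so the achieved values will be lower under the same assumptions.

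**What to change.** 1. In section 9.4.2, stratify the primary comparison by index reason (overdose vs other opioid-related visit), using an exact stratified test of Mantel-Haenszel type and a stratified risk difference with its 95% CI. In section 9.4.1, name index reason as a covariate in the adjusted logistic model. Define it from the reason for ED admission, which section 8.1 has staff verify before recruitment, so that it does not depend on who conducts the interview.
2. In section 9.4.7, replace the present statement with one supportive table: the arm difference with 95% CI within each index-reason group, and the interaction estimate. Label it as not powered. Section 9.2 says that the planned analyses were conducted; if so, label the stratified test and the table as post hoc.
3. Align the title, synopsis and section 2.1 with section 5.1, and state that the pooled result is not an effect specific to overdose survivors. Any remark about that group should cite its own row of the table, with its imprecision. Section 6.3 repeats the eligible conditions without endocarditis, so it must be reconciled with section 5.1.

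The cost is a few sentences and one small table, with no new data collection. The downside is imprecise stratum estimates that may be over-read, and slightly more analysis work.
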